### 12.2. Monitoring

Monitoring will be carried out as required following a risk assessment and as documented in the current version of the trial monitoring plan. NCTU will be in regular contact with the site research team to check on progress and address any queries that they may have. The trial team will check incoming CRFs for compliance with the protocol, data consistency, missing data and timing. Sites will be asked for missing data or clarification of inconsistencies or discrepancies. Additional on-site monitoring visits may be triggered, for example by poor CRF return, poor data quality, excessive number of participant withdrawals or deviations. If a monitoring visit is required, NCTU will contact the site to arrange a date for the proposed visit and will provide the site with written confirmation. Investigators will allow NCTU trial staff access to source documents as requested.

### 12.3. Audit and Inspection

The PI will permit trial-related monitoring, quality checks, audits, ethical reviews, and regulatory inspection(s) at their site, providing direct access to source data/documents. The PI will comply with these visits and any required follow up. Sites are also requested to notify NCTU of any MHRA inspections.

The Trial Master File and evidence of audits will be made available upon request for regulatory inspections.

### 12.4. Notification of Serious Breaches

In accordance with Regulation 29A of the Medicines for Human Use (Clinical Trials) Regulations 2004 (and its amendments) the Sponsor of the trial is responsible for notifying the licensing authority in writing of any serious breach of the conditions and principles of GCP in connection with that trial or the protocol relating to that trial, within 7 days of becoming aware of that breach.

For the purposes of this regulation, a “serious breach” is a breach which is likely to effect to a significant degree the safety or physical or mental integrity of the subjects of the trial, or the scientific value of the trial. Sites are therefore requested to notify NCTU of any suspected trial-related serious breach of GCP and/or the trial protocol. Where NCTU is investigating whether a serious breach has occurred, sites are also requested to cooperate with NCTU in providing sufficient information to report the breach to the MHRA where required and in undertaking any corrective and/or preventive action. Serious and persistent non-compliance with the protocol and/or GCP, and/or poor recruitment could potentially meet the criteria of a Serious Breach and sites may be

suspended from further recruitment. Any major problems identified during monitoring may be reported to TMG, Trial Steering Committee, Sponsor, the REC and the relevant regulatory bodies. This includes reporting serious breaches of GCP and/or the trial protocol to the REC and MHRA.

### 13. End of Trial Definition

The end of trial will be the final database lock. This will allow sufficient time for the completion of protocol procedures, data collection and data input. NCTU will notify the MHRA and REC that the trial has ended within 90 days of the end of trial. If the decision to terminate the trial early has been made, NCTU will inform the MHRA and REC within 15 days of that decision. NCTU will provide them with a summary of the clinical trial report within 12 months of the end of trial.

### 14. Statistical Considerations

#### 14.1. Sample size calculation

We have powered the trial to establish the non-inferiority of desogestrel compared to the COCP in settling problem bleeding. Data from previous studies [10, 23] show that approximately 90% of implant users would experience significant improvement in bleeding pattern with COCP or ulipristal treatment within the 90 days reference period. To be conservative we have used a reference group proportion of 85%. There are no validated minimum clinically important differences for improvement in bleeding pattern, but our sexual health clinical experts and patient representatives advised that, due to its advantages, adoption of desogestrel would be recommended even if it has a slightly less improvement rate in bleeding pattern of at least 75%. This represents an absolute non-inferiority margin of 10% and was judged to be a clinically relevant margin. A sample size of 276 per arm (552 total) would be required to achieve 90% power to detect non-inferiority of desogestrel compared to COCP within a non-inferiority margin of 10% based on one-sided 2.5% significance level, 1:1 allocation, and a likelihood score test statistic (Farrington and Manning) assuming the actual between-group difference in improvement proportion is zero. Allowing for up to 20% missing primary outcome data, we plan to randomise 690 participants.

#### 14.2. Definition of Outcome Measures

##### 14.2.1. Primary outcome

Patient-reported resolution of problem bleeding will be measured by participants' self-determination that their bleeding pattern improved using a 5-point Likert scale (improved significantly, improved slightly, no change, worsened slightly, worsened significantly). The outcome will be dichotomised into a response of "significantly improved" versus any other response. Patient perception of their bleeding pattern will be measured every 30 days during a 90-day reference period, with the last measurement (asked at day 90) treated as the primary time-point.

##### 14.2.2. Secondary outcomes

**Table 10-Secondary outcomes**

Outcome Measure	Definition or derivation
Participant's self-reported significant improvement in the bleeding pattern.	At day 30, 60 and 90 as for primary outcome

Participant's self-reported non-worsening of the bleeding pattern	The 5-point Likert scale will be dichotomised into a response of "improved significantly" or "improved slightly" or "no change" versus "worsened slightly" or "worsened significantly"
Participant self-reported bleeding pattern.	Total number of days, within the 90-day window, of: 
 
- no bleeding
 
- spotting
 
- bleeding
 

Longest duration of consecutive non-bleeding (no bleeding or spotting) whole days for each 30-day period within the 90 days.	Longest consecutive number of days with responses of no bleeding or spotting, in 90 days
Time to longest episode of consecutive non-bleeding whole days	Time to the first day of the longest consecutive number of days with responses of no bleeding or spotting, over the 90 days.
Number of bleeding episodes	Number of episodes with one or more consecutive days of reported bleeding, bounded by bleed-free days, within the 90 days
Duration of bleeding episodes	Number of episodes of 2, 3 (etc, to maximum reported) consecutive days with reported bleeding.
Participant-reported side effects	Measured at baseline and day 30, 60 and 90 to assess whether a participant has experienced the side effect and if so the extent of the side effects so that they can be compared to previous timepoints. (Using no/yes "mild", "moderate" or "severe"
Participant reported adherence to trial treatment	Responses will be categorised as all (90/90 pills), most (63-89/90), some (36-62/90), few (1-35/90) and none (0/90). 'Few' and 'None' categories would be classed as treatment non-adherence.
Participant reported discontinuation/removal of their implant	Proportion of participants who report removal of the implant and time to this event.
Participant reported EQ-5D-5L and ICECAP-A	Derived according to published scoring systems.

Participant reported treatment and healthcare usage	Participant Questionnaire
Intention to continue of their allocated treatment after unblinding	Participant Questionnaire

### 14.3. Analysis of Outcome Measures

The reporting of the trial will be in accordance with the CONSORT extension to reporting of non-inferiority and equivalence randomised trials [24]. Full details of the statistical analysis will be provided in the Statistical Analysis Plan, which will be finalised and approved by the Trial Steering Committee (TSC) prior to database lock.

Comparative analysis will be performed for the primary outcome on both the intention to treat (ITT) population and some version of the per-protocol (PP) population (preferably complier average causal effect (CACE) analysis, if feasible/identified), as a protection against the ITT's possible increased risk of falsely claiming noninferiority (type I error). Primary estimand will be the treatment policy estimand (i.e., ITT population- analysing data on all randomised participants according to the randomised groups irrespective of subsequent compliance with the treatment allocation) with CACE (or per-protocol) results used to check the consistency. Full definition and cut-off for compliance will be specified in the Statistical Analysis Plan (SAP).

For the primary outcome, a two-sided 95% confidence interval for the between-group difference in proportion of participants reporting significant improvement will be constructed by fitting a mixed-effect logistic regression model, adjusting for site as a random effect and other minimisation factors as fixed effects. The model will include outcome data from all the 3 timepoints (30, 60, and 90 days) and will include treatment by time interaction to obtain the treatment effect at each timepoint with 90 days as the primary contrast. Estimates of model-adjusted difference in proportions and 95% confidence intervals will be obtained by contrasts of average marginal predictions in the fitted model. Non-inferiority of desogestrel will be inferred if the lower bound of this interval lies within the non-inferiority margin of 10%. Missing data for primary outcome will be dealt with through maximum likelihood estimation using mixed-effect model which will use all available follow-up data. Intercurrent events such as discontinuation of assigned treatment or treatment switching, if any, will be dealt with through treatment policy strategy for the primary analysis.

Between-group comparison of secondary outcomes will be based on an appropriate regression model for the outcome, in the generalised linear mixed model framework adjusting for the minimisation factors and baseline outcome measure for continuous variables, if available. Adverse events will be presented descriptively and will be summarised according to the treatment received. All other planned sensitivity and exploratory analyses will be described in the SAP.

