
Statistical methods
	
For the primary outcome, a two-sided 95% confidence interval for the between-group difference in proportion of people reporting significant improvement will be constructed by fitting a mixed-effect logistic regression model, adjusting for site as a random effect and other minimisation factors as fixed effects. The model will include outcome data from all the 3 timepoints (30, 60, and 90 days) and will include treatment by time interaction to obtain the treatment effect at each timepoint with 90 days as the primary contrast. Non-inferiority of desogestrel will be inferred if the lower bound of this interval lies within the non-inferiority margin of 10%. Analysis will be performed on both the intention to treat (ITT) and per-protocol (PP) population, with ITT being the primary inference. Between-group comparison of secondary outcomes will be based on an appropriate regression model for the outcome, in the generalised linear mixed model framework adjusting for same variables as the primary analysis.

Health Economics
	
Resource Use: The main resources to be monitored include:
 
 
1. The costs associated with treatment (provision of desogestrel and COCP).
 

WPD 3.1\_Protocol Template\_Version 3.1\_20-Apr-2023

[figure not shown]
2. Time and resource use incurred in sexual and reproductive health research (SRH) settings associated with clinical examination, additional treatments and monitoring during the follow up period and to treat any adverse events.
3. Costs associated with discontinuation of the implant.
4. Costs associated with general practitioner (GP) attendances, A&E visits and other National Health Service (NHS) secondary care.
5. Any other health and social care resource use.
6. Costs such as those incurred by implant users and their families (e.g. associated with problem bleeding), will also be captured to allow personal family costs ed as a secondary analysis.

Information on unit costs or prices will be sourced to attach to each resource use item, to enable an overall cost per participant to be calculated (e.g. Unit Costs of Health and Social Care and NHS Reference Costs).

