**Table 8-Withdrawal type and procedure post randomisation**

Withdrawal type	Withdrawal procedure	Use of data
Withdrawal from trial treatment	Any participant that requests to discontinue trial treatment will be marked as withdrawn from treatment on the trial database but will be asked to continue to complete questionnaires if willing. Information on reason for stopping trial treatment will be recorded by the site if given, and patient care will continue as part of standard clinical practice.	Any data collected prior to participant withdrawal will be retained and used in the analysis.
Removal of implant	Any participant who notifies the trial or site team that their implant has been removed during their participation in the trial would be withdrawn from the trial and unblinded to their treatment allocation to	Any data collected prior to participant withdrawal will be retained and used in the analysis.

	inform their ongoing contraceptive care. Participants would not be required to complete any further questionnaires or daily diaries but would be followed up for safety outcomes for 7 days following stopping of their trial treatment.	
Withdrawal from daily bleed diary	Any participant that requests to discontinue from daily bleed diary will be marked as withdrawn from diary collection on the trial database and no further MyCap notifications will be sent. Withdrawal from the daily diary does not withdraw from questionnaire completion.	Any data collected prior to participant withdrawal will be retained and used in the analysis.
Withdrawal from follow up questionnaires	Any participant that requests to discontinue from trial questionnaires will be marked as withdrawn from questionnaire collection on the trial database and no further contact relating to questionnaires will be made. Withdrawal from questionnaires does not withdraw from daily diary completion.	Any data collected prior to participant withdrawal will be retained and used in the analysis.
Withdrawal from long-term follow-up	Any participant that withdraws consent for the long term follow-up will be recorded within the database and no long term follow-up data will be collected.	Any data collected prior to participant withdrawal will be retained and used in the analysis.

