#### 14.4.4. Procedures for missing, unused and spurious data

Every effort will be made to follow up all participants up to the primary endpoint, however, as missing data is inevitable, we will employ statistical techniques for handling missing data for the primary outcomes under the Missing At Random assumption such as further adjustment in the mixed model for variables predictive of missingness. For the primary analysis, only minimisation variables will be adjusted for as covariates and we do not expect any to be missing as they are required for the participant to be allocated.

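### The primary repeated-measures logistic model names site as its only random effect, so, fitted as written, it cannot deliver the maximum-likelihood handling of missing day-90 answers that the protocol claims for it.

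*Protocol*

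**What the plan says.** Section 14.3 describes the primary analysis as a mixed-effect logistic regression. On the data it says: "The model will include outcome data from all the 3 timepoints (30, 60, and 90 days) and will include treatment by time interaction". On how the minimisation variables enter it says: "adjusting for site as a random effect and other minimisation factors as fixed effects". The Trial Summary repeats both statements. Neither place names a participant-level effect or a within-participant correlation.

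The day-90 risk difference and its interval are to be "obtained by contrasts of average marginal predictions in the fitted model". Section 14.3 then makes the missing-data claim: "Missing data for primary outcome will be dealt with through maximum likelihood estimation using mixed-effect model which will use all available follow-up data".

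Section 14.4.4 offers techniques "under the Missing At Random assumption such as further adjustment in the mixed model for variables predictive of missingness", but adds: "For the primary analysis, only minimisation variables will be adjusted for as covariates".

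Table 8 in section 8.4.2 withdraws a participant whose implant is removed: "Participants would not be required to complete any further questionnaires or daily diaries".

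**The concern.** In a repeated-measures model, a participant's early answers inform a missing later answer only through a term that links that person's answers. A site effect does not do this, because it is shared by everyone at the site. With a separate treatment effect at each visit, the day-30 and day-60 answers of someone who misses day 90 add essentially nothing to the day-90 estimate beyond shared site and covariate coefficients. The other possible route, adjusting for predictors of missingness, is closed for the primary analysis by section 14.4.4.

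This matters because missing day-90 answers are plausibly related to response. Implant removal ends the questionnaires, and section 1 gives problem bleeding as the most commonly reported reason for discontinuing the implant. Table 12 also withdraws participants who start certain other hormonal treatments. Section 14.1 allows for 20% missing primary outcomes. The single interval compared with the 10% margin could therefore be shifted by a mechanism that the plan says it has dealt with.

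**Working it through.** **1. The plan's own sample size.** Inputs from section 14.1: 85% in both arms, margin 0.10, one-sided 2.5%, power 90%, Farrington-Manning test. The proportions constrained to the null are 0.887 and 0.787.

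n = [1.960 × √(0.887×0.113 + 0.787×0.213) + 1.2816 × √(2×0.85×0.15)]² / 0.10² = 275.7

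That is 276 per arm, 552 in total, and 552/0.8 = 690. The stated figures reproduce, and nothing below changes them.

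**2. What the written model estimates.** With no participant term, the likelihood treats the three answers as independent given site and covariates. Taking zero site variance and no covariates for simplicity, the day-90 estimate in each arm equals the proportion improved among those observed at day 90.

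**3. Assumed inputs (not in the protocol).**
- True rates at days 30/60/90: 65/75/85% on COCP and 55/65/75% on desogestrel, so the true difference is -10 points, on the margin.
- Answers generated with a participant random intercept, SD 1, 2 or 3 on the logit scale.
- Day-60 non-improvers four times as likely to miss day 90 as improvers, with the same rule in both arms and set to give 20% missing on COCP. The improvers' probability is 0.20/(0.25×4 + 0.75) = 0.114, and the non-improvers' is 4 × 0.114 = 0.457.
- The same rule on desogestrel gives 0.35×0.457 + 0.65×0.114 = 23.4% missing.
- 345 randomised per arm.

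**4. Worked case, SD 2.** Integrating over the participant effect, the chance of improvement at day 90 is:
- COCP: 0.9185 if improved at day 60, 0.6446 if not.
- Desogestrel: 0.8665 if improved at day 60, 0.5337 if not.

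The observed day-90 rates are then:
- COCP: [0.75×0.9185×0.8857 + 0.25×0.6446×0.5429]/0.800 = 0.872 (truth 0.85)
- Desogestrel: [0.65×0.8665×0.8857 + 0.35×0.5337×0.5429]/0.7657 = 0.784 (truth 0.75)

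The difference is -8.8 points. Its standard error is √(0.872×0.128/276 + 0.784×0.216/264.2) = 0.0323. The chance of declaring non-inferiority is Φ[(-0.0881 + 0.10)/0.0323 - 1.96] = Φ(-1.59) = 5.6%.

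**5. All cases with the true difference at -10 points.** Each cell gives the estimated difference in points and the chance of declaring non-inferiority.

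| Day-90 missingness | SD 1 | SD 2 | SD 3 |
|---|---|---|---|
| Same response-dependent rule in both arms | -9.4; 3.7% | -8.8; 5.6% | -8.4; 7.2% |
| 20% per arm, response-dependent on desogestrel only | -8.8; 5.4% | -7.2; 13.1% | -6.2; 21.6% |
| 20% per arm, response-dependent on COCP only | -10.9; 1.3% | -12.2; 0.4% | -13.1; 0.2% |
| 20% per arm, unrelated to response | -10.0; 2.5% | -10.0; 2.5% | -10.0; 2.5% |

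With equal true rates of 85% and the same rule in both arms, both observed rates rise equally and the difference stays at 0.

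**6. With a participant term.** Maximum likelihood with a participant random intercept, and predictions integrated over it, returns -10.0 points in every case in the table. Here the fitted model is also the model that generated the data, so this shows that the mechanism can be repaired. It does not guarantee exact recovery in practice.

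**The case against.** The strongest reply is that the protocol does not say site is the only random effect. The clause can be read as describing how the four minimisation variables enter, without listing the full covariance structure. The claim to use all available follow-up makes sense only if some within-participant dependence was intended. Section 14.3 also defers full details to the statistical analysis plan, which is not shown and may add the term.

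Part of this stands. A participant term is not expressly excluded, and a reader who infers that the protocol has ruled one out goes beyond the text. But this is more than a detail left open. The protocol states a random-effect structure in two places, restricts the covariates, and attaches a missing-data claim that the stated structure cannot deliver. An analyst following it literally obtains the weaker analysis.

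Two stronger readings are tempting and should not be drawn.
- **The bias always favours non-inferiority.** It does not. It is conservative if response-dependent loss is confined to COCP, it cancels with equal true rates and a common rule, and it is absent if missingness depends only on arm, site and minimisation factors.
- **The risk difference will be computed with the random effect set to zero, which would shrink it.** The protocol proposes nothing of the kind. Its wording on average marginal predictions points to averaged predictions. The only request here is to state the integration explicitly once a participant term is present.

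**Conclusion.** The point holds for the model as the protocol writes it: the stated primary model and the stated missing-data method do not fit together. The size is conditional. With the true difference at the margin and one response-dependent rule in both arms, the site-only model moves the estimate by about 0.6 to 1.6 points towards non-inferiority and raises the false non-inferiority rate from 2.5% to about 4% to 7%. Across all the cases computed, the shift runs from about 3 points against desogestrel to about 4 points in its favour.

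The visit-specific rates before day 90, the within-participant correlation and the fourfold missingness ratio are all assumptions, and the documents give no figures for them. The site-only model was evaluated in large samples without site variance or covariates, which approximates the planned fit.

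**What to change.** In section 14.3 and the Trial Summary, and in the statistical analysis plan, name a participant-level random intercept in addition to the site effect. Another likelihood-based model that carries within-participant dependence would also serve. State that the average marginal predictions behind the day-90 risk difference are integrated over the random effects. Treatment, time, their interaction and the minimisation factors stay as they are.

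The cost is about one sentence in each place and slightly more computing. Sample size, data collection and the margin do not change.
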